12. ADVERSE EVENTS

Adverse events will be described and graded according to the Common Terminology Criteria for Adverse Events (CTCAE) v5.0. A copy of the CTCAE v5.0 is found at the following web site:

http://ctep.cancer.gov/protocolDevelopment/electronic_applications/ctc.htm#ctc_50

Symptoms and events associated with SARS-CoV-2 infection will be scored as per the SARS-CoV-2 infection symptom score (Table 2) and the Ordinal Scale for Clinical Improvement (Table 4). These findings should not be reported as Adverse Events.

12.1. Definitions

Adverse Event (AE)

An AE is any untoward medical occurrence associated with the use of a drug in humans, whether or not considered drug related.

An AE can therefore be any unfavorable and unintended sign (including an abnormal laboratory finding, for example), symptom, or disease temporally associated with the use of a medicinal (investigational) product, whether or not related to the medicinal (investigational) product.

An abnormal laboratory value will be considered an AE if it qualifies as such based on CTCAE v5.0.

Throughout the course of the study, every effort should be made to remain alert to possible AEs. Subjects should be encouraged to report AEs spontaneously or in response to general, nondirected questioning.

With the occurrence of an AE, the primary concern is the safety of the subject. Appropriate management of the AE should always be the first priority.

Suspected Adverse Reaction

Defined as any adverse event for which there is a reasonable possibility that the drug caused the adverse event. For the purposes of IND safety reporting “reasonable possibility” means there is evidence to suggest a causal relationship between the drug and the adverse event. Suspected adverse reaction implies a lesser degree of certainty about causality than adverse reaction, which means any adverse event caused by the drug.

Life-Threatening Adverse Event or Life-Threatening Suspected Adverse Reaction

An adverse event or suspected adverse reaction is considered “life-threatening” if, in the view of either the investigator or sponsor, its occurrence places the patient or subject at immediate risk of death. It does not include an adverse event or suspected adverse reaction that, had it occurred in a more severe form might have caused death.

Serious Adverse Event (SAE) or Serious Suspected Adverse Reaction

The terms “serious” and “severe” are not synonymous. Adverse events classified as “serious” have defined regulatory requirements. Those classified as “severe” do not have defined regulatory requirements unless they are also classified as “serious”.

The term “severe” is often used to describe the intensity of a specific event (as in mild, moderate, or severe myocardial infarction); the event itself, however, may be of relatively minor medical significance (such as severe headache).

An AE is classified as “serious” based on the criteria outlined below. Seriousness (not severity) defines the regulatory reporting obligations.

An adverse event or suspected adverse reaction is considered “serious” if in the view of either the investigator or sponsor, it results in any of the following outcomes:

- Death
- A life-threatening adverse event
- In-patient hospitalization or prolongation of existing hospitalization
- Persistent or significant incapacity or substantial disruption to conduct normal life functions
- A congenital anomaly/birth defect
- Intervention to prevent any one of the other outcomes listed above (based on medical judgment)

Important medical events that may not result in death, be life-threatening, or require hospitalization may be considered serious when, based on appropriate medical judgment, they may jeopardize the subject and may require medical or surgical intervention to prevent one of the outcomes listed above. Examples of such medical events are allergic bronchospasm requiring intensive treatment in the emergency room or at home, blood dyscrasias, convulsions that do not result in in-patient hospitalization, or the development of drug dependency or drug abuse.

Unexpected Adverse Event or Unexpected Suspected Adverse Reaction

An AE or suspected adverse reaction is considered “unexpected” if it is not listed in the Investigator’s Brochure or is not listed in the Investigator’s Brochure at the specificity and severity observed.

Serious and Unexpected Adverse Event or Suspected Adverse Reaction

Any AE or suspected adverse reaction that occurs during the subject’s participation in the study that meets the criteria for both serious and unexpected as defined above is considered a serious and unexpected AE or suspected adverse reaction.

12.2. Adverse Event Reporting Period

The AE reporting period for this study is continuous and begins at the time of randomization to study treatment and ends on Study Day 29.

In addition, any known untoward event that occurs subsequent to the AE reporting period that the Investigator assesses as related to the investigational medication should also be reported as an AE.

All AEs (both serious and nonserious) must be followed until resolution or until a stable clinical endpoint is reached. All measures required for AE management and the ultimate outcome of the AE must be recorded in the source documentation and in the eCRF.

12.3. Treatment Emergent Adverse Events

Treatment-emergent AEs are defined as those that begin or worsen after the start of study drug administration.

12.4. Recording of AEs

All AEs will be documented in the appropriate section of the eCRF.

NOTE: Symptoms and events associated with SARS-CoV-2 infection will be scored as per the SARS-CoV-2 infection symptom score ([Table 2](#)) and the Ordinal Scale for Clinical Improvement ([Table 4](#)). These findings should not be reported as Adverse Events.

In the event that the electronic data capture (EDC) system cannot be accessed and a SAE or serious suspected adverse reaction has occurred, a paper SAE report form will be available to be completed and faxed or emailed to the Sponsor or their designee.

The following will be recorded for each AE in the eCRF:

- A description of the AE in medical terms. Whenever possible, a diagnosis should be given when signs and symptoms are due to common etiology (e.g., cough, runny nose, sneezing, sore throat, and head congestion should be reported as “upper respiratory infection”)
- Start date
- Stop date
- The severity (i.e., grade) as assessed by the Investigator according to the definitions in the CTCAE v5.0.
- If the AE is not specifically listed in the reference above, the following grades should be used:
 - Grade 1 Mild; asymptomatic or mild symptoms; clinical or diagnostic observations only; intervention not indicated
 - Grade 2 Moderate; minimal, local or noninvasive intervention indicated; limiting age-appropriate instrumental ADL (Activities of Daily Living)
 - Grade 3 Severe or medically significant but not immediately life threatening; hospitalization or prolongation of hospitalization indicated; disabling; limiting self-care ADL
 - Grade 4 Life-threatening consequences; urgent intervention indicated
 - Grade 5 Death related to AE
- The causal relationship to study drug as assessed by the Investigator; the decisive factor in the documentation is the temporal relation between the AE and the study drug.
- Action(s) taken (e.g., study drug administration interrupted, study drug not administered, none, unknown).
- The outcome (e.g., recovered/resolved, not recovered/not resolved, recovering/resolving, recovered/resolved with sequelae, fatal, unknown).

- Whether it caused the subject to discontinue the study.

If in any 1 subject the same AE occurs on several occasions (unless the AE is continuous and of stable grade), the AE in question will be documented and assessed at each occurrence.

Should a pregnancy of a female participant or a partner of a male participant occur, it must be reported and recorded in the eCRF. Pregnancy in itself is not regarded as an AE unless there is suspicion that an investigational product may have interfered with the effectiveness of a contraceptive medication.

The outcome of all pregnancies (spontaneous miscarriage, elective termination, normal birth, or congenital abnormality) must be followed up and documented even if the subject was discontinued from the study.

All reports of congenital abnormalities/birth defects are SAEs. Spontaneous miscarriages should also be reported and handled as SAEs. Elective abortions without complications should not be handled as AEs.

12.5. Assessing Relationships of AE to Study Drug

The Investigator must record his/her opinion concerning the relationship of the AE to study therapy on the AE eCRF. [Table 3](#) provides guidance for assigning relationship to the study drug.

Table 3: Relationship of Adverse Event to the Administration of the Study Drug

Unrelated	There is not a temporal relationship to study drug or there is a reasonable causal relationship between another drug, concurrent disease, or circumstance and the AE. The AE is clearly not related to study drug.
Unlikely	There is a temporal relationship to study drug, but there is not a reasonable causal relationship between the study drug and the AE. The AE is doubtfully related to study drug.
Possibly	There is a reasonable causal relationship between the study drug and the AE. The AE may be related to study drug.
Probably	There is a reasonable causal relationship between the study drug and the AE. The AE is likely related to the study drug.
Definitely	There is a causal relationship between the study drug and the AE. The AE is clearly related to the study drug.

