7.2.5 Adverse Event Summaries

All AEs (serious and non-serious) occurring after randomization and before the end of study, regardless of relationship to study drug, will be included and classified by SOC and PT using MedDRA.

For TEAEs, the following will be summarized and presented:

- i. An overall summary of TEAEs, which includes:
 - a. the number and percentage of subjects experiencing a TEAE
 - b. the number and percentage of subjects experiencing a TEAE by strongest relationship to study drug
 - c. the number and percentage of subjects experiencing a TEAE by greatest severity
 - d. the number and percentage of subjects experiencing a treatment-emergent SAE
 - e. the number and percentage of subjects experiencing a TEAE leading to death
 - f. the number and percentage of subjects experiencing a TEAE leading to study withdrawal
- ii. the number and percentage of subjects experiencing a TEAE by SOC and PT.
- iii. the number and percentage of subjects experiencing a potentially related TEAE by SOC and PT, where a potentially related TEAE is defined as any TEAE with a causal relationship to study drug assessed as 'Possibly Related', 'Probably Related', or 'Definitely Related'.
- iv. the number and percentage of subjects experiencing a TEAE by SOC, PT and the strongest relationship to study drug
- v. the number and percentage of subjects experiencing a TEAE by SOC, PT and the greatest severity
- vi. the number and percentage of subjects experiencing a treatment-emergent SAE by SOC and PT
- vii. the number and percentage of patients experiencing a TEAE leading to death by SOC and PT

viii. the number and percentage of subjects experiencing a TEAE leading to study withdrawal by SOC and PT

In the overall summary of TEAEs table (i), besides tabulating the number and percentage of subjects, the total number of TEAE episodes will also be provided. If a subject has repeated episodes of a particular TEAE, all episodes will be counted in the summary table.

In the remaining summary tables, the incidence of TEAEs will be calculated by dividing the number of subjects who have experienced the event by the total number of subjects. Thus, the incidence of TEAEs is shown in terms of the total number of subjects and not in terms of the total number of episodes. If a subject has repeated episodes of a particular TEAE, only the most severe episode, or the episode with the strongest causal relationship to study drug, will be counted in the summary tables.

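### The causality rows in Protocol Table 3 overlap, so an event that both study drug and COVID-19 could reasonably have caused can be graded Unrelated and drop out of the potentially related TEAE table

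*Protocol*

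**What the plan says.** Protocol Section 12.5 asks the Investigator to record an opinion on relationship to study drug, and says that Table 3 "provides guidance for assigning relationship to the study drug". Four of its five rows matter here.

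- *Unrelated* is met if there is no temporal relationship, **or** if "there is a reasonable causal relationship between another drug, concurrent disease, or circumstance and the AE". The row closes with "The AE is clearly not related to study drug".
- *Unlikely* is met if there is a temporal relationship but no reasonable causal link to study drug.
- *Possibly* and *Probably* have the same criterion: "There is a reasonable causal relationship between the study drug and the AE". Only their closing lines differ; for *Possibly* it is "The AE may be related to study drug".

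Two other sections bear on the same judgement. Section 12.4 says of the causality assessment that "the decisive factor in the documentation is the temporal relation between the AE and the study drug". Section 12.1 defines a suspected adverse reaction as "any adverse event for which there is a reasonable possibility that the drug caused the adverse event".

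SAP 7.2.5 then uses the grade. In item iii, "a potentially related TEAE is defined as any TEAE with a causal relationship to study drug assessed as" possibly, probably or definitely related. Items i.b and iv display TEAEs by strongest relationship.

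**The concern.** An attribution scale should give one level of relatedness for a given set of facts. In this trial the difficult case is foreseeable. Inclusion criterion 1 requires a positive SARS-CoV-2 test, so a competing concurrent disease is present in every subject. Section 5.4 describes a dose-dependent fall in FEV1, lowest about 30 minutes after dosing, so the drug acts on the organ that the disease affects.

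A respiratory AE soon after a dose may then have two reasonable causes. If two investigators can follow the table and grade it *Unrelated* and *Possibly*, the potentially related TEAE table depends on which row each of them applied. The protocol allows up to 15 centers, which leaves room for inconsistent grading. Tolerability is a secondary objective and SAP Section 7 plans no formal safety testing, so the descriptive tables carry the safety conclusion.

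**Working it through.** No figure in the plan is involved, so the check is one of logic. Three yes/no facts describe an event:

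- T: there is a temporal relationship to study drug.
- D: there is a reasonable causal relationship with study drug.
- A: there is a reasonable causal relationship with another drug, disease or circumstance.

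The criteria of Table 3, read literally and leaving the closing lines aside, are:

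- *Unrelated* = (not T) or A
- *Unlikely* = T and not D
- *Possibly* = *Probably* = D

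*Definitely* asserts an outright causal relationship and is not needed here. Counting *Possibly* and *Probably* as one level gives:

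| T | D | A | Levels met |
|---|---|---|---|
| yes | yes | yes | Unrelated; Possibly/Probably |
| yes | yes | no | Possibly/Probably |
| yes | no | yes | Unrelated; Unlikely |
| yes | no | no | Unlikely |
| no | yes | yes | Unrelated; Possibly/Probably |
| no | yes | no | Unrelated; Possibly/Probably |
| no | no | yes | Unrelated |
| no | no | no | Unrelated |

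Four of the 8 combinations meet more than one level. The two with D but not T will be rare, because a drug cause is seldom reasonable without plausible timing. The third row matters little for reporting, since both of its levels lie outside SAP item iii. The first row is the one at issue: a post-dose event that both drug and COVID-19 could reasonably have caused. It meets a level that item iii drops and a level that item iii keeps, and Table 3 gives no tie-break.

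The same first-row event can be set against the other sections:

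- **Section 12.4.** If timing is decisive, a close temporal relationship should point towards the drug. Table 3 allows *Unrelated* (through A) or, where D is absent, *Unlikely*, even though T holds. The two sections conflict.
- **Section 12.1.** A reasonable possibility of drug cause is not removed by a second possible cause. The event is a suspected adverse reaction there, yet can be *Unrelated* in Table 3.

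If the event is graded *Unrelated*, its reach in SAP 7.2.5 is:

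- Item iii: the event is dropped.
- Items i.b and iv: it is still shown, under the *Unrelated* label unless the subject has a more strongly related TEAE in that count.
- Items ii and v, and vi to viii where the event is serious, fatal or leads to withdrawal: it is retained, since none of these filters on relatedness.

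One table is exposed. With the proposed wording, *Unrelated* becomes (not T) or (A and not D), taking D as a reasonable possibility that the drug contributed. The first row then meets *Possibly/Probably* only.

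**The case against.** The strongest reply is that the *Unrelated* row ends by saying the event is clearly not related to study drug. A dual-cause event does not fit that line and does fit the closing line of *Possibly*. A careful investigator would choose *Possibly*, and Table 3 is guidance for an opinion. This stands as far as it goes: the table permits *Unrelated* and does not compel it. It does not cure the defect, because the closing line conflicts with the criterion just before it.

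A second reply is that Sections 12 and 12.4 already keep symptoms and events associated with SARS-CoV-2 infection out of AE reporting. An event put down to COVID-19 may never reach Table 3. This also stands. The point covers only events that are recorded as AEs, and rewording Table 3 would not bring back those kept out earlier.

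A third reply is that the main safeguards do not use attribution. SAP 7.3 summarizes FEV1 change by arm, including categories of reduction. Under Section 14.4 the DSMB reviews any imbalance in AEs between the arms, and under Section 12.6 any SAE is reported within 24 hours. All of this stands. In addition, Section 7.10.2 describes the earlier falls in lung function as usually asymptomatic, so the number that would become AEs is unknown.

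A reader might infer that suspected-reaction reporting runs on the Table 3 grade. Neither Section 12.1 nor Section 12.6 says so. A reader might also see a flat contradiction with Section 12.1. That section defines a safety-reporting term and Table 3 is an attribution scale, so what the text supports is a mismatch in dual-cause cases.

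**Conclusion.** The point holds as a defect of definition with limited reach. Read literally, the rows of Table 3 are not mutually exclusive: a reasonable alternative cause alone satisfies *Unrelated*, even when study drug is also a reasonable cause. *Possibly* and *Probably* cannot be told apart by their criteria. The table conflicts with Section 12.4 and, for dual-cause events, does not match Section 12.1.

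The consequence is that some recorded AEs **can** be absent from SAP 7.2.5 item iii. It would be tempting to say that Table 3 makes every event COVID-19 could explain *Unrelated*, or that related respiratory events will be understated because all subjects are infected. The documents do not support either. The row asks for a reasonable causal relationship, the grade remains the Investigator's opinion, and the same event qualifies for *Possibly*.

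The number of events affected cannot be computed. It depends on how many dual-cause events are recorded as AEs and on how investigators resolve the overlap. No efficacy analysis and no stated figure changes. The conclusion assumes that the criteria are read as written and that no other site instruction, outside these documents, sets an order among the rows.

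**What to change.** 1. In Table 3, reword *Unrelated* so that an alternative cause counts only when there is also no reasonable possibility that study drug contributed.
2. Give *Possibly* and *Probably* different criteria, for example by whether another cause is about as likely as the drug or clearly less likely.
3. In Section 12.4, reconcile the phrase that makes timing decisive with the reasonable-possibility test in Section 12.1, so that timing is one element of the judgement.
4. Optionally, add one SAP table by arm of TEAEs starting on the calendar day of each dose or the next day, regardless of attribution. Section 12.4 lists a start date and no onset time, so a finer interval would need a change to the eCRF. Because Section 7.11 allows the Day 3 and Day 6 visits to move by a day, state how an event is assigned when two such intervals meet.

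The cost is protocol wording, a short training note to sites and, if wanted, one table built from data already collected. The downside is somewhat more events graded possibly related, in both blinded arms.

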12.6. Reporting Serious or Unexpected AEs

Any SAE or serious suspected adverse reaction that occurs during the course of the study will be reported **within 24 hours after the site becomes aware of the event.**

All SAE reporting will adhere to the United States Code of Federal Regulations (CFR), specifically 21 CFR 312.32 for Investigational New Drugs, and applicable local regulations. The Investigator will notify the governing IRB/Ethics Committee of any SAEs and safety reports per IRB/Ethics Committee reporting requirements.

12.7. Follow-up of Adverse Events

All AEs (both serious and non-serious) should be followed until resolution or until a stable clinical endpoint is reached. All measures required for AE management and the ultimate outcome of the AE must be recorded in the source document and the eCRF.

Any SAE or serious suspected adverse reaction follow-up information requested should be provided in a timely manner. The additional information may include copies of hospital reports, autopsy reports, or other relevant documents.

13. STATISTICAL METHODS

13.1. Sample Size Determination

The trial size of 100 subjects (50 PUL-042 inhalation solution: 50 placebo) was chosen based on clinical considerations. The rates of infection to adequately estimate a sample size for a statistically significant result are unknown.

Enrolled subjects will be randomized with equal probability to receive blinded treatment consisting of either PUL-042 or placebo.

13.2. Subject Populations

Intention to Treat (ITT)

The ITT population will include all randomized subjects who receive at least one dose of experimental treatment (i.e., PUL-042 or Placebo).

The ITT population will be the primary data source used to address study objectives.

Safety Population

The Safety population is the same as the ITT population. The Safety population will be the data source used to evaluate the safety and tolerability of experimental treatment for this study.

13.3. Primary Objective

To determine the efficacy of PUL-042 Inhalation Solution in decreasing the severity of COVID-19 in subjects: 1) who have documented SARS-CoV-2 infection, and 2) if receiving oxygen, should have pulse oximetry $\geq 93\%$ on 3 liters per minute of oxygen or less delivered by nasal prongs (Ordinal Scale for Clinical Improvement 4 or less) at the time of enrollment.

The primary endpoint for this study will be the difference in the proportion of patients with clinically meaningful worsening of COVID-19 within 28 days from the start of experimental therapy, as indicated by an increase of at least 2 points on the Ordinal Scale for Clinical Improvement.

The Ordinal Scale for Clinical Improvement is a 9-point scale that measures disease severity. For this study, an increase of 2 or more points is considered meaningful worsening of disease ([Table 4](#)). This endpoint considers changes in disease severity that are observed at any time over the course of this study.

This endpoint will be evaluated as the difference in binomial proportions under the null hypothesis of no difference between randomized treatment groups. Full details of the planned analysis will be included in the Statistical Analysis Plan that will be developed for this study.

The Ordinal Scale for Clinical Improvement to be used in this study is derived from a draft scale proposed by the World Health Organization⁹ for clinical improvement as presented below:

Table 4: Ordinal Scale for Clinical Improvement (Derived from draft WHO scale)⁹

Descriptor	Score
No clinical or virological evidence of infection	0
Infected but no limitation of activities	1
Limitation of activities	2
Hospitalized not requiring oxygen therapy (SpO ₂ > 93% on room air)	3
Oxygen by mask or nasal prongs	4
Non-invasive ventilation or high-flow oxygen	5
Intubation and mechanical ventilation	6
Ventilation + additional organ support- pressors, RRT, ECMO	7
Death	8

It is possible that medically justified treatment and or procedures cannot be implemented due to the unavailability of equipment (e.g., scarcity of ventilators). In such cases, the data recorded in the eCRF should reflect the prescribed circumstances rather than the reality. For example, if clinical evaluation of a patient indicates the need for mechanical ventilation when no ventilator is available, that patient should be scored as 6 – “Intubation and mechanical ventilation” not as a lower score on the Ordinal Scale for Clinical Improvement.

